8.3.1.22 Change from Baseline in PsAID-12 total score

Method for derivation of PsAID-12 can be found in [Section 8.2.1.13](#).

The proportion of subjects achieving a total score of PsAID-12 \leq 4 - Patient acceptable symptom state (PASS), the proportion of subjects achieving a decrease of 3 or more points from Baseline on the total score (for subjects with minimal score of 3 at Baseline), the change from Baseline in the total score and in the individual scores for each PsAID-12 domain, will be analyzed at Week 4, 16, 24, 36, 52 (the proportions of subjects achieving PASS will also be analyzed at Baseline).

8.3.1.23 Change from Baseline in the Psoriatic Arthritis Quality of Life (PsAQoL) total score

PsAQoL is a disease specific Health-Related Quality of Life questionnaire comprised of 20 items. Each item is scored as 0 for “not true” or 1 for “true”, so that the score ranges from 0 to 20 with higher scores indicating worse health-related quality of life.

If 6 or less item responses are missing, the missing responses will be imputed with the mean of available responses to calculate a total score. If more than 6 items responses are missing, the total score will be left missing.

Change from Baseline in PsAQoL total score will be analyzed at Week 4, 16, 24, 36, 52.

8.3.1.24 Change from Baseline in the SF-36 PCS and MCS scores, as well as the 8 domain scores (Physical Functioning, Role Physical, Bodily Pain, General Health, Vitality, Social Functioning, Role Emotional, and Mental Health)

Scoring instructions of SF-36 norm-based T-scores for the 8 domains and the SF-36 PCS and MCS are described in [Section 8.2.1.3](#).

Change from Baseline in SF-36 individual domain scores, MCS and PCS scores will be analyzed at Week 4, 16, 24, 36, 52.

8.3.1.25 Change from Baseline in Functional Assessment of Chronic Illness Therapy (FACIT)—Fatigue subscale score

The FACIT-Fatigue is a 40-item measure that assesses self-reported fatigue and its impact upon daily activities and function over the past 7 days. The scale consists of 5 subscales (physical well-being, social/family well-being, emotional well-being, functional well-being, and fatigue). The fatigue subscale is the only one used in this study. It is composed of 13 items, all scored from 0 (Not at all) to 4 (Very much). The FACIT-Fatigue subscale score ranges from 0 to 52 with 0 being the worst possible score and 52 being the best possible score. To obtain a score from 0 to 52, all negatively worded questions must be recoded, so that responses range from worst (0) to the best (4) outcome.

Items 1 to 6 and 9 to 13 are negatively framed questions for which the coding needs to be reversed before deriving the score.

The FACIT-Fatigue subscale score is obtained by summing up the responses of all reversed / non reversed items with equal weight. In cases where some answers are missing, a total score is rescaled from the score of the answered items, so long as more than 50% of the items (ie, at least 7 of 13) were answered.

The formula to derive the FACIT-Fatigue subscale score is then:

$$\text{FACIT-Fatigue subscale score} = 13 \times \frac{\sum \text{Score of items}}{\text{number of item answered}}$$

The minimum clinically important difference for FACIT-Fatigue subscale score in patients with PsA was determined to be a 4-point positive change.

Change from Baseline in FACIT-Fatigue subscale score, as well as the proportion of subjects with minimum clinically important difference for FACIT-Fatigue subscale score in subjects with FACIT-Fatigue subscale score ≤ 48 at Baseline, will be analyzed at Week 4, 16, 24, 36, 52.

8.3.1.26 Change from Baseline in Work Productivity and Activity Impairment Questionnaire—Specific Health Problem (WPAI-SHP) v2.0 adapted to PsA scores

The WPAI-SHP is a subject-reported questionnaire that assesses subject's employment status, work absenteeism, work impairment while working (presenteeism), overall work and daily activity impairment attributable to a specific health problem.

Five out of 6 items of the WPAI-SHP are regrouped into the 4 dimensions (absenteeism, presenteeism, work productivity and activity impairment) with scores expressed as percentage, where higher numbers indicate greater impairment and less productivity, ie, worse outcomes, as described in the WPAI-SHP scoring rules.

The scoring rules for the WPAI-SHP are as follows:

Questions:

- [REDACTED]

Scores:

- Percent work time missed due to problem from the target disease:

$$100 \times \frac{Q2 \text{ hours}}{(Q2 \text{ hours} + Q4 \text{ hours})}$$

- Percent impairment while working due to problem from the target disease:

$$100 \times \frac{Q5 \text{ Score}}{10}$$

- Percent overall work impairment due to problem from the target disease:

$$100 \times \left[\frac{Q2 \text{ hours}}{(Q2 \text{ hours} + Q4 \text{ hours})} + \left(\left(1 - \frac{Q2 \text{ hours}}{(Q2 \text{ hours} + Q4 \text{ hours})} \right) \times \frac{Q5 \text{ score}}{10} \right) \right]$$

- Percent activity impairment due to problem from the target disease:

$$100 \times \frac{Q6 \text{ Score}}{10}$$

To make data consistent and amenable to statistical analysis, the following counting rules will be applied to handle out of range and ambiguous answers of the WPAI-SHP. These rules will be

applied prior to conducting any type of statistical analysis of the data. Due to the inter-relation between certain questions of the WPAI-SHP, the priority order for implementing these specific counting rules is as in the listed order below.

- Employment status:
 - If (Q1=missing) and (Q2>0 or Q3>0 or Q4>0), then Q1=YES.
- Hours missed due to psoriatic arthritis:
 - If Q1 = NO, then Q2 = missing.
 - If (Q2 =0 or missing) and Q1 = missing, then Q2=missing.
- Hours missed due to other reasons:
 - If Q1 = NO, then Q3 = missing.
 - If (Q3 =0 or missing) and Q1 = missing, then Q3=missing.
- Hours actually worked:
 - If Q1 = NO, then Q4 = missing.
 - If (Q4 =0 or missing) and Q1 = missing, then Q4=missing.
- Work productivity:
 - If Q1 = NO, then Q5 = missing.
 - If (Q5 =0 or missing) and Q1 = missing, then Q5=missing.
 - If Q4=0, then Q5 = missing.

In the listings, the original values will be kept and displayed.

The WPAI-SHP scores are based on 1-item (presenteeism, activity impairment), 2-items (absenteeism) and multiple items (overall work productivity). A score cannot be calculated if there is a missing response to the corresponding item.

A negative number will indicate a reduction in the score/improvement for subjects.

The change from Baseline score is derived as post Baseline score minus Baseline score. A negative change score indicates a reduction in the score/improvement for the subject.

The change from Baseline in scores will be analyzed at Week 16, 24, 52.

The analysis of WPAI-SHP scores will be performed on observed cases only.

8.3.1.27 Responses to the EuroQol-5 Dimensions-3 Level (EQ-5D-3L), change from Baseline in VAS score

The Euro-Quality of Life 5-Dimensions 3 Level version (EQ-5D-3L) health questionnaire provides a descriptive profile and a single index value for health status (using a VAS).

The instrument is composed of a 5-item health status measure (mobility, self-care, usual activities, pain/discomfort, anxiety/depression) and a VAS. Each of the 5 health states is divided

into 3 levels (no problem, some or moderate problems, and extreme problems) and is scored as 1, 2, and 3, respectively. These scores are referred as “utility scores”.

The EQ-5D VAS records the respondent's self-rated health status on a vertical 20cm scale, 0 to 100 graduated (0=worst imaginable health status, 100=best imaginable health status).

The response in each of the 5 items of the EQ-5D-3L and the values and the changes in VAS from Baseline will be presented at Week 4, 16, 24, 36, 52.

8.3.1.28 Change from Baseline in Patient's Global Assessment of Arthritis (PGA-arthritis) and Physician's Global Assessment of Arthritis (PhGA-Arthritis)

The physician's global assessment of arthritis (PhGA-arthritis) and the patient's global assessment of arthritis (PGA-arthritis) are clinical outcomes based on visual analog scales (VAS) ranged from 0 to 100 (in mm).

- PGA-Arthritis: Subjects will assess the impact of their arthritis pain in answering the following question “Considering all the ways your arthritis affects you, please mark a vertical line on the scale below to show how you are feeling today.” The subject should be asked to consider their arthritis symptoms and functional capacity in their response to this question. Subjects will score PGA-Arthritis in using a VAS where 0 is “very good, no symptoms” and 100 is “very poor, severe symptoms.”
- PhGA-Arthritis: The investigator will assess how the subject's overall arthritis appears at the time of the visit using a numerical rating scale where 0 is “very good” and 100 is “very poor”. This assessment will be based through the following question: “The Patient's arthritis at this time is: “Please mark a vertical line on the scale below to assess the overall status of the subject's arthritis signs and symptoms and the functional capacity of the subject.”

Values and changes from Baseline in PhGA-Arthritis and PGA-Arthritis will be analyzed at Week 2, 4, 8, 12, 16, 20, 24, 28, 32, 36, 44, 52.

8.3.2 Analyses of other efficacy endpoints

Unless specified above, all other efficacy variables will be analyzed for all subjects:

- In by-visit tables, for the following treatment groups: Placebo/BKZ160 mg Q4W, BKZ 160mg Q4W, ADA 40mg Q2W.
- on the RS, for the overall study period (until Week 24 for the Week 24 analysis).

8.3.2.1 Time to ACR20/50/70 response

The time to ACR20/50/70 response will be successively analyzed:

- For the DBP, on the 3 treatment groups (for the Week 24 analysis).
- For the overall study period, on the 3 treatment groups (for the Week 52 analysis) They will be estimated and presented using the Kaplan Meier (KM) product limit method for each of treatment groups.

The KM plots of time to ACR20,50,70 response will be presented by treatment group. The line will start at 0 and will increase over time, representing time to achieving the response (reversed KM estimates).

The median time to response, including the 2 sided 95% CI, will be calculated for each treatment group.

For the analysis on the DBP, the hazard ratio of BKZ vs. placebo as well as the corresponding 95% CI and p-value will be displayed (using SAS® PROC PHREG stratified by region and bone erosion at Baseline)

Comparisons of BKZ vs. placebo will be analyzed based on a log-rank test stratified by region and bone erosion at Baseline (0, ≥ 1) (considering that the same stratification factors have been retained for the primary efficacy analysis). This comparison will be performed using SAS® PROC LIFETEST on subjects from both treatment groups.

The time to ACR20/50/70 endpoints will be analyzed using OC data.

8.3.2.2 Other endpoints (excluding time to ACR20/50/70 response)

For the binary variables, the following estimand structure (composite estimand) will be defined:

- Population = Subjects enrolled according to the protocol-specified inclusion/exclusion criteria and randomized to IMP.
- Subject-level outcome = The given variable and time point being summarized.
- IE handling = An IE is defined as discontinuation of study treatment prior to the time point being summarized. A composite strategy will be implemented in which a positive clinical outcome is defined as achieving the given variable at the specified time point and not discontinuing study treatment through that time point.
- Population-level summary measure = Unadjusted proportion of responder.

Subjects who have an IE, which will be considered associated to a treatment failure, will be considered as non-responders. Any missing data will also be considered as non-responders (NRI approach). For categorical variables, the worst-category will be imputed similarly instead of non-response.

For the continuous variables, the following estimand (hypothetical estimand) will be defined:

- Population = Subjects enrolled according to the protocol-specified inclusion/exclusion criteria and randomized to IMP.
- Subject-level outcome = The given variable and time point being summarized.
- IE handling = An IE is defined as discontinuation of study treatment prior to the time point being summarized. A hypothetical strategy will be implemented in which outcomes for subjects without an IE are as observed at the given time point, and outcomes for subjects with an IE are treated as though they had completed the randomized study treatment through the time point being summarized. A MI strategy will be used to impute data following an IE.
- Population-level summary measure = Unadjusted mean.

The analysis of other continuous efficacy variables will be performed according to the above estimand, using MI-MCMC/ monotone regression as imputation method for missing data for all visits up to Week 24 for the Week 24 analysis and all visits up to Week 52 for the Week 52 analysis (similarly as in [Section 8.2.2](#)).

The other efficacy variables will also be summarized based on OC and the modified composite estimand (for binary variables) and summarized by visit for all treatment groups as detailed below:

For binary endpoints using:

- The number and proportion of responders using the NRI approach.
- The mean proportion of responders in the multiple imputed datasets and the 95% CI (modified composite estimand). For ACR50 response at post-Week 16 visits for subjects responding at Week 16, the same imputed data as generated in the context of the analysis of the primary efficacy endpoint will be used.
 - For enthesitis and dactylitis free-state based on the pooled data of PA0010 and PA0011 subjects (for subjects in the BKZ 160mg Q4W and the Placebo group), the MI will be performed on the pooled dataset (using data from Baseline, Week 4, 8, 12 and 16) the same way as described in [Section 4.2.2.2](#), but with the following covariates in that order for each SAS® PROC MI: region (North America, Western Europe and Eastern Europe in that order) and study-id (“1” for PA0011 and “0” for PA0010).
 - For enthesitis based on LEI, the MI will be run on all subjects and results reported for subjects with LEI>0 at Baseline ; for other binary variables derived from continuous value(s), the MI will be run on the subset of subjects (if applicable) for which the variable will be reported (ie: for LDI and Tender dactylitis count in the context of PASDAS calculation, on subjects with LDI>0 at Baseline)
 - For ACR50 based on Week 16 Baseline, the MI will be run on Week 16 and post-week 16 values, on the ATBS for the Placebo group. Week 16 value will be considered as the Baseline value regardless of whether the Placebo subjects switched to BKZ on a later visit.
 - For PASI90 based on Week 16 Baseline, the MI will be run on W16 and post-week 16 values, on the ATBS for the Placebo group on subjects with PSO involving at least 3% of BSA at Week 16. Week 16 value will be considered as the Baseline value regardless of whether the Placebo subjects switched to BKZ on a later visit.
- The observed number and proportion of responders on subjects with observed data

For categorical endpoints (ie, EQ-5D-3L dimensions score, DAPSA state, PASDAS categories) using:

- The number and percentage by endpoint category using the NRI approach (as performed for the primary analysis of the primary endpoint with the exception that the NRI is replaced by the worst category imputation)

- The mean percentage and corresponding 95% CI by endpoint category in the multiple imputed datasets (modified composite estimand). Regardless of imputed values, the value of the categorical endpoint after IE are by default set to the worst category (ie: High Disease Activity for DAPSA state)
- The observed number and percentage by category on subjects with observed data.

For continuous endpoints, on absolute values and changes from Baseline (or ratio from Baseline for hs-CRP) using:

- The mean (with geometric mean for hs-CRP and its 95% CI), SE, median, minimum, and maximum in the multiple imputed datasets (hypothetical estimand) (except for WPAI-SHP scores).
 - For the change from baseline in LDI, LEI and SPARCC based on the pooled data of PA0010 and PA0011 subjects (for subjects in the BKZ 160mg Q4W and the Placebo group), the MI will be performed on the pooled dataset (using data from Baseline, Week 4, 8, 12 and 16) the same way as described in [Section 4.2.2.2](#), but with the following covariates in that order for each SAS® PROC MI: region (North America, Western Europe and Eastern Europe in that order) and study-id (“1” for PA0011 and “0” for PA0010).
 - For LEI, the MI will be run on all subjects and results reported for subjects with LEI>0 at Baseline ; for other continuous variables derived from continuous value(s), the MI will be run on the subset of subjects (if applicable) for which the variable will be reported (ie: for LDI, on subjects with LDI>0 at Baseline)
 - For Tender dactylitis count in the context of PASDAS calculation, if the MI does not converge, a conservative approach will be used by first imputing a value of 1 for all joints with missing tenderness score.
- The observed number of observations (n), the mean (with the geometric mean for hs-CRP), SD, median, CV (geometric CV for hs-CRP), minimum, and maximum.

For ACR20, ACR50, ACR70, PASI75, PASI90, and PASI100 responders over time, a line plot by treatment group will be produced.

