2.2.1.3 Other efficacy variables

Change from Baseline variables evaluated during the Double-Blind Treatment Period (DBP) are relative to the Baseline (first dose) visit. For subjects randomized to placebo who switch to BKZ 160mg Q4W at the Week 16 visit, change from Baseline variables during the Active Treatment-Blind Period (ATP) may be evaluated relative to both the Baseline (first dose) visit and to the Week 16 visit (first dose of BKZ).

For simplicity, “change from Baseline” is used below for all such variables. More details will be provided below in [Section 3.3](#).

The other efficacy variables listed below will be summarized for all timepoints except for the previously defined primary and secondary efficacy variables which will be also summarized separately at Week 16 (and at Week 4 and 16 for PASI90).

The following other efficacy variables will be assessed (all timepoints not specified in [Section 2.2.1.1](#) and [2.2.1.2](#) are exploratory):

- Time to ACR20, ACR50, and ACR70 response from Baseline (Day 1)
- ACR20, ACR50, and ACR70 response
- PASI75, PASI90, and PASI100 response in the subgroup of subjects with PSO involving at least 3% BSA at Baseline
- Composite endpoint composed of ACR50 and PASI90 in subjects with PSO involving at least 3% BSA at Baseline
- Composite endpoint composed of ACR50 and PASI100 in subjects with PSO involving at least 3% BSA at Baseline
- Proportion of Psoriatic Arthritis Response Criteria (PsARC) responders
- Psoriatic Arthritis Disease Activity Score (PASDAS) categories
- Change from Baseline in the PASDAS
- Proportion of ACR50 responders at Week 16 and maintaining response at Week 52
- MDA response
- Very Low Disease Activity (VLDA) response
- Proportion of subjects with an IGA score of 0 (clear) or 1 (almost clear) and at least a 2-grade reduction from Baseline in the subset of subjects with psoriatic skin lesions at Baseline
- Disease Activity Index for Psoriatic Arthritis (DAPSA) score categories

- Change from Baseline in DAPSA score
- Change from Baseline in the Disease Activity Score-28 based on C-reactive protein (DAS28[CRP])
- Change from Baseline in all individual ACR core components:
 - Swollen Joint Count (SJC)
 - Tender Joint Count (TJC)
 - HAQ-DI
 - PtAAP
 - Physician's Global Assessment of Psoriatic Arthritis (PhGA-PsA)
 - Patient's Global Assessment of Psoriatic Arthritis (PGA-PsA)
 - hs-CRP

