3.3 Definition of Baseline values

A Baseline value for a subject is defined as the latest measurement for that subject up to and including the day of first administration of IMP (Visit 2 by default), unless otherwise stated.

By default, for randomized subjects for whom no start date of treatment is available, the Baseline value will be considered as the last available value prior to the randomization date.

If a Baseline assessment is taken on the same day as first administration of IMP, it is eligible to be used as the Baseline value, even in the case that the time of the assessment is recorded as taking place after the time of first administration of IMP. This is considered acceptable as this measurement is still the best representation of the Baseline value of the given assessment since it is highly unlikely that the IMP could have an impact on any measurement in such a short period of time. However, such cases should be rare as study center personnel are instructed to do all assessments at the Baseline visit prior to administering IMP. One exception to this rule is plasma concentration. If Baseline plasma concentration is measured at a time after the first administration of IMP, then it should not be eligible to be considered as a Baseline plasma concentration. Such cases should be discussed with the quantitative clinical pharmacologist.

If a Baseline measurement is missing or not collected, and a Screening value is available, the Screening value will be utilized as Baseline instead. If no measurement is available prior to receiving IMP, then the Baseline value is treated as missing.

Baseline values for component scores should be computed using components from the same visit where the relevant measurements were recorded prior to dosing. For example, if the Screening visit has all the components, but the Baseline visit is missing one or more components, the Baseline value for the component score should be calculated using the Screening visit values.

When the time of first dose is derived, it should be based on the first injection of IMP, regardless of whether it is an active treatment.

Chest x-ray performed within 3 months before the Screening visit is considered as Baseline measurement.

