For subjects who switch treatment from placebo to BKZ at Week 16 (Visit 10), an additional Baseline value (called Week 16 Baseline) will be defined for efficacy variables. The Week 16 value will be considered as the Baseline value regardless of whether the Placebo subjects switched to BKZ on a later visit.

The variables listed below will be analyzed relative to the Week 16 Baseline value for the ATP, for timepoints after Week 16:

- PASI90 response
- ACR50 response.

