8.3.1.2 ACR20, ACR50 and ACR70

Method for derivation of ACR50 can be found in [Section 8.1.1](#). ACR20 and ACR70 will be derived similarly except that they will be based on a 20% and on 70% improvement from Baseline.

ACR20, ACR50 and ACR70 responses will be analyzed at Week 2, 4, 8, 12, 16, 20, 24, 28, 32, 36, 44, 52.

For the placebo group, ACR50 response will be presented both based on the Day 1 Baseline and on the Week 16 Baseline (on the ATS, for the ATP, for subjects switching to BKZ at Week 16).

8.3.1.3 PASI75, PASI90 and PASI100 response (in subjects with PSO involving at least 3% of BSA at Baseline)

Method for derivation of PASI score can be found in [Section 8.2.1.2](#).

PASI75, PASI90, PASI100 are binary variables equal to 1 if the percentage improvement from Baseline in the PASI scores is $\geq 75\%$, $\geq 90\%$, 100% and 0 if the percentage improvement from Baseline is $< 75\%$, 90%, 100%.

PASI75, PASI90, PASI100 as well as the PASI score and the change from Baseline for subjects with PSO involving at least 3% of BSA at Baseline will be analyzed at Week 2, 4, 8, 12, 16, 20, 24, 28, 32, 36, 52.

For the placebo group, PASI90 responses will be determined both based on the Day 0 Baseline and on Week 16 Baseline (on the ATS, for the ATP, for subjects switching to BKZ at Week 16).

8.3.1.4 Composite endpoints composed of ACR50 and PASI90 and ACR50 and PASI100 responses (subjects with PSO involving at least 3% of BSA at Baseline)

The composite endpoint composed of ACR50 and PASI90 is a binary variable equal to 1 for subjects responding to ACR50 (ACR50=1) and PASI90 (PASI90=1).

The composite endpoint will be equal to 0 if ACR50=0 or PASI90=0 regardless of whether any of the 2 endpoints is missing.

The same rules as above will be applicable for the composite endpoint on ACR50 and PASI100.

The composite endpoints will be missing if both endpoints are missing or if any of the 2 is missing and the other one equal to 1.

Each endpoint (ACR50 and PASI90 or PASI100) will be imputed separately before deriving the composite endpoint.

The composite endpoints for subjects with PSO involving at least 3% BSA at Baseline will be analyzed at Week 2, 4, 8, 12, 16, 20, 24, 28, 32, 36, 52.

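### PASI90 from the Week 16 Baseline is tied to BSA of at least 3% at Baseline in Section 8.3.1.3 but at Week 16 in Section 8.3.2.2, so its NRI/OC and MI summaries can use different subjects

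*SAP*

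**What the plan says.** Section 2.2.1.3 lists the variable as "PASI75, PASI90, and PASI100 response in the subgroup of subjects with PSO involving at least 3% BSA at Baseline". The heading of Section 8.3.1.3 repeats the limit: "PASI75, PASI90 and PASI100 response (in subjects with PSO involving at least 3% of BSA at Baseline"). Under that heading, the section says that for the placebo group "PASI90 responses will be determined both based on the Day 0 Baseline and on Week 16 Baseline". For the second version it adds only that the analysis is on the ATS, for the ATP, in subjects switching to BKZ. It gives no separate BSA condition.

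Section 8.3.2.2 describes the MI for this second version and runs it "on subjects with PSO involving at least 3% of BSA at Week 16". Two sub-bullets earlier, the same list gives a general rule for binary variables derived from continuous values: "the MI will be run on the subset of subjects (if applicable) for which the variable will be reported". The NRI and observed-case bullets in 8.3.2.2, and the Table 4-4 row for the extra by-visit tables from the Week 16 Baseline, carry no BSA condition.

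Section 3.3 keeps the two baselines apart. Baseline is the "latest measurement for that subject up to and including the day of first administration of IMP". For placebo switchers, "an additional Baseline value (called Week 16 Baseline) will be defined for efficacy variables".

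**The concern.** The document attaches two BSA conditions, at visits 16 weeks apart, to one endpoint. NRI, OC and MI summaries are set side by side to show how much the handling of missing data matters. If the MI set is chosen at Week 16 and the others at first dose, the summaries can differ with no data missing at all.

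The subjects in whom the sets differ are not a random sample. Those with at least 3% BSA at first dose but less at Week 16 improved on placebo and start BKZ with little skin disease. PASI90 from Week 16 asks them for a further 90% fall from a low score. If the score is already 0, the percent improvement has a zero denominator. Section 8.1.1 has a zero-baseline rule for ACR components, but Section 8.2.1.2 has none for PASI. Under Section 4.2.2.1 a response that cannot be derived counts as non-response, so a subject who is clear at Week 16 and stays clear on BKZ would be reported as a failure.

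**Working it through.** The SAP gives no figure for this endpoint, so there is nothing to reproduce. The check has three parts.

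**1. Conditions side by side**

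| Place | BSA condition for PASI90 from the Week 16 Baseline |
|---|---|
| 8.3.1.3 heading | at least 3% at Baseline |
| 8.3.1.3 text on the Week 16 version | none beyond the heading |
| 8.3.2.2, NRI bullet | none |
| 8.3.2.2, observed-case bullet | none |
| 8.3.2.2, MI sub-bullet | at least 3% at Week 16 |
| Table 4-4 row | none |

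The only stated condition available to NRI and OC is the heading of 8.3.1.3. Because Section 3.3 defines Baseline by first dose, that is a different set from the MI set. It also breaks the rule in 8.3.2.2 that the MI subset is the reported subset.

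**2. What a low starting PASI implies**

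In the formula of Section 8.2.1.2 the smallest regional weight is 0.1 and the smallest non-zero severity and area scores are 1. The smallest non-zero PASI is therefore 0.1 × 1 × 1 = 0.1, and with complete items scores move in steps of 0.1. PASI90 needs a score of at most 0.1 × the starting score. If the starting score is below 1.0, this limit is below 0.1 and only a score of exactly 0 qualifies. If the starting score is 0, the ratio is undefined.

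Subjects who fall below 3% do exist: Section 8.2.1.10 reports some with at least 3% BSA at Baseline and less than 3% at Week 4 and Week 16, without naming the arm. Section 2.4.2 plans for a placebo PASI90 rate of 10% at Week 16.

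**3. Illustration of size**

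Inputs from the SAP: 280 placebo subjects (2.3.1) and 60% with at least 3% BSA (2.4.2), so 280 × 0.60 = 168. Assumed, because the SAP gives no values: the share of the 168 below 3% at Week 16 (m subjects), a response of r = 60% in the others, and of q = 0% or 30% in those below 3%.

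Rate in the Baseline-defined set = [(168 − m) × r + m × q] / 168. Gap to the Week 16 set = (m/168) × (r − q).

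| Share below 3% | m | Week 16 set | Rate, q = 0 | Gap (points) | Rate, q = 30% | Gap (points) |
|---|---|---|---|---|---|---|
| 5% | 8 | 160 | 57.1% | 2.9 | 58.6% | 1.4 |
| 10% | 17 | 151 | 53.9% | 6.1 | 57.0% | 3.0 |
| 20% | 34 | 134 | 47.9% | 12.1 | 53.9% | 6.1 |
| 30% | 50 | 118 | 42.1% | 17.9 | 51.1% | 8.9 |

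For example, at 30%: (118 × 0.60 + 50 × 0)/168 = 70.8/168 = 42.1%, and 60 − 42.1 = 17.9. The base of 168 counts all planned placebo subjects; the ATS will be somewhat smaller, but the gap depends on the share m/168 and not on the total.

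**The case against.** The strongest reply is that the SAP already implies a single population. The only statement specific to this version is the Week 16 condition in 8.3.2.2, and the same list says MI is run on the reported subset. Section 3.3 also treats the Week 16 value as the baseline for these subjects. On that reading, Baseline in the heading of 8.3.1.3 means Week 16 for this version, all three summaries agree, and a starting PASI of 0 should not occur, since at least 3% of the skin is involved. This has weight: the NRI/OC population is inferred from a heading and from silence elsewhere. A reader might infer that the SAP fixes different populations for NRI, OC and MI, but it does not say so outright. What remains is that Section 3.3 names the two baselines separately and 8.3.1.3 itself contrasts them, so a programmer following the text would obtain two sets.

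Three further inferences are tempting and are not supported:

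- That subjects who rise to 3% BSA by Week 16 enter only the MI version. This requires post-Baseline PASI in subjects below 3% at first dose. The SAP does not show that it is collected, and Section 8.2.1.10 limits post-Baseline IGA to subjects with at least 3% at Baseline.
- That subjects below 3% cannot respond. Non-response is forced only at a Week 16 PASI of 0. Others with a low score can respond, though below 1.0 only by clearing completely.
- That a treatment comparison is biased. This is a one-group descriptive summary, outside the hierarchy of Table 4-5 and not named for nominal testing in 8.3.2.3. OC has its own denominator by design.

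**Conclusion.** The inconsistency is in the current text and the point stands in a limited form. As written, NRI/OC and MI for PASI90 from the Week 16 Baseline can use different subjects. The NRI/OC set can include subjects already below 3% BSA, among them any with an undefined percent improvement that NRI turns into non-response.

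The size cannot be known from the SAP. The range of about 1 to 18 points rests wholly on assumed values: 5-30% of subjects below 3% at Week 16, 60% response in the others and 0-30% in those below 3%. It shows that the choice of set can matter; it is not an estimate. The consequence is confined to one exploratory by-visit summary of the Placebo/BKZ group. The primary analysis and the H3 test of PASI90 at Week 16, which uses the first-dose Baseline, are unaffected. The correction is still worth making, because it can change a reported rate and costs little.

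**What to change.** In Section 8.3.1.3, state that for PASI90 from the Week 16 Baseline the NRI, OC and MI summaries all use placebo-randomised ATS subjects whose psoriasis covers 3% or more of BSA at Week 16. Add that percent improvement is not evaluated, and the subject is excluded, if the Week 16 PASI is 0. Mirror the condition in Section 8.3.2.2, at the level of the endpoint and not only in the MI sub-bullet, and in the Table 4-4 row. This adopts the visit that 8.3.2.2 already uses, satisfies its rule that MI is run on the reported subset, and removes most of the zero-denominator problem.

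The cost is a sentence or two and a subset flag. The denominator becomes somewhat smaller: in the illustration, 160 to 118 in place of 168.
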